1.1 Protocol Amendment: Summary of Changes

Previous Protocol Versions

Protocol	Date
Original	24 February 2016
Amendment 0.02	25 April 2016
Administrative Change 1 (GLOBAL)	30 June 2016
Amendment 0.02.01 (ROW)	22 May 2017
Amendment 0.02.01.01 (ROW)	23 July 2018

The purpose of this amendment is to:

- Revise the contact details on the front page of the protocol.
Rationale: To change the phone number to Sponsor/Emergency Contact [name].
- Revise Section 5.3.1.1 Study Procedures – Extended Access Phase
Rationale: To indicate that if a subject in the extended access phase of this study continues to derive benefit from Venetoclax after the 2-year extension, then per PI's assessment, subjects who are transferring to the venetoclax extension study, Study M19-388, may remain in Extended Access for up to additional 1 year or until the extension study is approved and initiated at the site, whichever is sooner.
- Update Appendix B – List of signatories.
Rationale: To replace [REDACTED] as the Study Project Manager with [REDACTED]. To replace [REDACTED] as the Sr. Medical Director with [REDACTED]. To remove [REDACTED] as the Group Project Director. GPD is no longer required for protocol signature. To add [REDACTED] as the Evidence Generation Medical Lead/Director. To replace [REDACTED] as the Study Project Manager with [REDACTED].
- Revise Appendix E Schedule of Extended Access Phase.
Rationale: To add an additional year to the Schedule of Extended Access Phase.

An itemized list of all changes made to this protocol amendment can be found in [Appendix J](#).

1.2 Synopsis

AbbVie Inc.	Protocol Number: M15-550
Name of Study Drug: Venetoclax (ABT-199, GDC-0199)	Phase of Development: 3b
Name of Active Ingredient: Venetoclax	Date of Protocol Synopsis: 12 October 2020
Protocol Title: Open-Label, Single Arm, Phase 3b, Multi-Center Study Evaluating the Efficacy of Venetoclax (ABT-199) in Relapsed/Refractory Subjects with Chronic Lymphocytic Leukemia (CLL) (VENICE I)	

Objectives:
 
Primary Objective: The primary objective of this study is to evaluate the efficacy of venetoclax monotherapy in subjects with relapsed or refractory chronic lymphocytic leukemia (CLL). The primary efficacy endpoint will be measured by complete remission rate (Complete Remission Rate [CR] and Complete Remission with Incomplete Marrow Recovery [CRi]; CR + CRi) as assessed by the investigator, of the subjects who have not been previously treated with B-cell receptor inhibitor (BCRi) therapy.
 
Secondary Objectives: The secondary objectives are to evaluate other efficacy parameters including the overall response rate (ORR), duration of overall response (DoR), time to progression (TTP), progression-free survival (PFS), overall survival (OS), and the CR rate in BCRi treated subjects. In addition, quality of life will be assessed using the following patient reported outcome (PRO) questionnaires: the EuroQoL 5 Dimensions (EQ-5D-5L) questionnaire, a measure of general health status, the Functional Assessment of Cancer Therapy – Leukemia Questionnaire (FACT-Leu), a leukemia-specific health related quality of life for acute and chronic disease, and the Functional Assessment of Chronic Illness Therapy-Fatigue Scale (FACIT-F).
 
The safety and tolerability of venetoclax in subjects with relapsed/refractory CLL will also be evaluated.
 
Exploratory Objectives: The exploratory objectives are to evaluate the level of Minimal Residual Disease (MRD) and the rate of MRD negativity in the peripheral blood.
	
Investigators: Multi-center	
Study Sites: Approximately 7 sites in the United States and approximately 67 sites globally.	
Study Population: Subjects with relapsed/refractory (R/R) CLL with or without the 17p deletion or TP53 mutation, including subjects with an unknown status, as well as R/R CLL subjects who have been previously treated with B-cell receptor inhibitor (BCRi) therapy.	
Number of Subjects to be Enrolled: Approximately 250 subjects	

Methodology:

This is a Phase 3b, single arm, open-label, multi-center study evaluating the efficacy of venetoclax in subjects with R/R CLL. All screening procedures must be performed within 28 days prior to initial study drug administration. A contrast computed tomography (CT) scan (or magnetic resonance imaging [MRI] if a CT with contrast is medically contraindicated) will be accepted if previously performed within 35 days prior to study drug administration, otherwise a CT scan (or MRI) must be performed within the screening period of 28 days. The starting dose of venetoclax is 20 mg once daily. The dose must be gradually increased over a 5-week period up to the daily dose of 400 mg. For all subjects, study visits will be conducted within 72 hours of dosing and on the first and second day of Week 1 and Week 2 during the dose titration phase. Beginning on Week 3, through Week 5, study visits will be conducted within 72 hours of dosing and on Day 1 of each week. Additional study visits on Day 2 of each week should be performed for subjects who continue to be at risk for TLS, based on investigator assessment. Study visits will be reduced to a monthly frequency at Week 8, and at Week 48, they will be reduced to every 3 months until the end of study treatment (Week 108). In countries where venetoclax is not commercially available, subjects who continue to derive benefit after 2 years of treatment may be able to extend their treatment for up to 2 additional years. If a subject in the extended access phase of this study continues to derive benefit from Venetoclax after the 2-year extension, then per PI's assessment, subjects who are transferring to the venetoclax extension study, Study M19-388, may remain in Extended Access for up to additional 1 year or until the extension study is approved and initiated at the site, whichever is sooner. A Disease Assessment for clinical response by physical exam and hematologic assessments will be performed at Screening, Week 24, Week 36 and Week 48. To confirm the response, a CT scan will be performed at Week 48 on all subjects. Biospecimens will be collected at designated time points throughout the study to conduct research to better characterize the disease. MRD assessments will be performed by using peripheral blood specimens at Week 1 Day 1 (baseline), Week 24 and Week 48. When confirming a CR or CRi status per 2008 Modified International Workshop for Chronic Lymphocytic Leukemia National Cancer Institute Working Group (IWCLL NCI WG) criteria with a bone marrow (BM) biopsy and aspirate, MRD assessment of the BM aspirate should also be performed. After treatment discontinuation, a final visit will be performed. Subjects will be followed for disease progression (if progression has not already occurred) and survival. Post-treatment follow-up calls will be performed every 6 months until discontinuation from the study. Survival information (i.e., the date and cause of death, post-treatment cancer therapies, date of progression etc.) will be collected. This period will continue for 2 years following discontinuation of venetoclax.

The Data Monitoring Committee (DMC) will review safety data intermittently according to the DMC charter. Subsequent reviews may be conducted based on recommendations from the DMC or requests from the Sponsor. Details of the DMC review will be presented in the DMC charter.

Diagnosis and Main Criteria for Inclusion/Exclusion:

Main Inclusion:

A subject will be eligible for study participation if he/she meets all of the following criteria:

1. Age \geq 18 years.
2. Eastern Cooperative Oncology Group (ECOG) performance score of \leq 2.
3. Subject has relapsed/refractory disease (received at least one prior therapy).

Diagnosis and Main Criteria for Inclusion/Exclusion (Continued):

Main Inclusion (Continued):

4. Diagnosis of CLL that meets published 2008 Modified IWCLL NCI-WG Guidelines and:
 - has an indication for treatment according to the 2008 Modified IWCLL NCI-WG criteria
 - has clinically measurable disease (lymphocytosis $> 5 \times 10^9/L$ and/or palpable and measurable nodes by physical exam and/or organomegaly assessed by physical exam)
 - subjects with or without the 17p deletion or TP53 mutation are eligible.
 - subjects who have received prior B-cell receptor inhibitor therapy are also eligible (up to 60 subjects total in the study will be enrolled).
5. Adequate bone marrow function as follows:
 - hemoglobin ≥ 8.0 g/dL
 - platelets $\geq 25,000/mm^3$ without any of the following:
 - transfusion support within 14 days of Screening
 - evidence of mucosal bleeding
 - known history of major bleeding episode within 3 months of Screening

Main Exclusion:

A subject will not be eligible for study participation if he/she meets any of the following criteria:

1. Subject has developed Richter's transformation or Prolymphocytic leukemia (PLL)
2. Subject has previously received venetoclax.
3. History of active malignancies other than CLL within the past 2 years prior to first dose of venetoclax, with the exception of:
 - adequately treated in situ carcinoma of the cervix uteri
 - adequately treated basal cell carcinoma or localized squamous cell carcinoma of the skin
 - previous malignancy confined and surgically resected (or treated with other modalities) with curative intent.
4. Active and uncontrolled autoimmune cytopenias (within 2 weeks prior to Screening), including autoimmune hemolytic anemia (AIHA) or idiopathic thrombocytopenic purpura (ITP), despite low dose corticosteroids.
5. Prior allogeneic stem cell transplant.

Investigational Product:	Venetoclax: 10 mg, 50 mg and 100 mg tablet
Doses:	Venetoclax will be administered orally once daily (QD), continuously. The starting dose of venetoclax is 20 mg QD. After 1 week of treatment at 20 mg QD, the dose will be escalated to 50 mg QD followed by subsequent increases, each after 1 week, to 100 mg QD, 200 mg QD and the target dose of 400 mg QD.
Mode of Administration:	Oral
Reference Therapy:	Not applicable.
Doses:	Not applicable.
Mode of Administration:	Not applicable.

Duration of Treatment: Subjects may continue receiving venetoclax for up to 2 years provided they continue to tolerate the drug, have no evidence of disease progression (based on investigator assessment), do not have unacceptable toxicity and do not meet any of the criteria for subject discontinuation. After treatment discontinuation, subjects will be followed for disease progression (if progression has not already occurred) and survival. Post-treatment calls will be performed every 6 months until discontinuation from the study. Survival information (i.e., the date and cause of death, post-treatment cancer therapies, date of progression etc.) will be collected. This period will continue for 2 years following discontinuation of venetoclax.

In countries where venetoclax is not commercially available, subjects who continue to derive benefit after 2 years of treatment may be able to extend their treatment for up to 2 additional years. If a subject in the extended access phase of this study continues to derive benefit after the 2-year extension and venetoclax is still not commercially available in their country, they may continue their treatment for 1 additional year. Per PI's assessment, subjects who are unable to transfer to the venetoclax extension study, Study M19-388, may remain in Extended Access for the additional 1 year or until the extension study is approved and initiated at the site, whichever is sooner. AbbVie will work with the investigator on a case by case basis to consider the potential continuation of venetoclax therapy.

Criteria for Evaluation:

Efficacy:

Disease response will be assessed by the investigator, based on laboratory results and physical examinations using the 2008 Modified IWCLL NCI-WG criteria for Tumor Response including CT imaging and bone marrow biopsy and aspirate for subjects with CR to confirm the response (or MRI in the case CT is medically contraindicated).

All measurable disease must be documented at Screening by physical examination, laboratory testing, and CT scan (or MRI in the case CT is medically contraindicated). During the study, clinical disease assessments will take place at Week 24, Week 36, and Week 48. To confirm the response, a CT scan will be performed at Week 48.

Minimal Residual Disease (MRD):

A peripheral blood specimen will be collected from all subjects at Week 1 Day 1 (baseline), Week 24 and Week 48 to determine the level of minimal residual disease. When confirming a CR/CRi status per 2008 Modified IWCLL NCI-WG criteria with a bone marrow biopsy and aspirate, MRD assessment of the BM aspirate should also be performed. The level of MRD and MRD negativity will be assessed. MRD negativity in the 2008 Modified IWCLL NCI-WG criteria is defined as the presence of less than one CLL cell per 10,000 leukocytes (or below 10^{-4}).

Pharmacokinetics:

A single pharmacokinetic (PK) blood sample will be collected from each subject and analyzed for plasma venetoclax concentration.

Safety:

Adverse event monitoring, vital signs, physical examination, and laboratory assessments will be evaluated.

The study analyses will be descriptive. All subjects participating in the study who received at least one dose of venetoclax will be included in the analyses unless otherwise noted in the separate, statistical analysis plan (SAP).

Statistical Methods (Continued):

Efficacy:

The following efficacy endpoints will be analyzed: Complete Remission rate (CR + CRi), Overall Response Rate (ORR), Duration of Overall Response (DOR), Duration of Progression-Free Survival (PFS) and Overall Survival (OS):

Complete Remission Rate (CR) and Complete Remission with Incomplete Marrow Recovery (CRi)

Defined as the proportion of subjects who achieved a CR or CRi (all subjects and previously BCRi treated subjects).

Overall Response Rate (ORR)

Defined as the proportion of subjects with an overall response (complete remission plus partial remission).

Duration of Response (DOR)

Defined as the number of days from the date of first response (per the 2008 Modified IWCLL NCI-WG criteria) to the date of disease progression. All disease progression will be included regardless whether the event occurred while the subject was taking venetoclax or had previously discontinued venetoclax.

Time to Progression (TTP)

Defined as the number of days from the date of first dose of venetoclax to date of disease progression. All disease progression will be included regardless whether the event occurred while the subject was taking venetoclax or had previously discontinued venetoclax.

Duration of Progression-Free Survival (PFS)

Defined as the number of days from the date of first dose of venetoclax to the date of disease progression or death, whichever occurs first. All disease progression will be included regardless whether the event occurred while the subject was taking venetoclax or had previously discontinued venetoclax.

Overall Survival (OS)

Defined as number of days from the date of first dose of venetoclax to the date of death.

Additional Exploratory Analyses Include:

Minimal Residual Disease (MRD) Level and Negativity Status:

The level of MRD and the rate of MRD negativity will be assessed in the peripheral blood of all subjects at Week 1 Day 1 (baseline), Week 24 and Week 48. MRD negativity will be defined as less than one CLL cell per 10,000 leukocytes (or below 10^{-4}). Additionally, bone marrow samples collected from subjects achieving CR/CRi will also be assessed for both the level of MRD and the rate of MRD negativity. Rate of MRD status will be defined as the proportion of subjects who have MRD negativity status. Ninety-five percent (95%) confidence intervals based on the binomial distribution will be provided. The relationship between venetoclax PK and efficacy parameters including MRD level and CR will be evaluated.

Pharmacokinetics:

An analysis of venetoclax plasma concentrations will be performed using a population PK modeling approach.

Statistical Methods (Continued):

Health Economic and Patient Reported Outcome (PRO) Measures:

Quality of life will be assessed by using the following PROs: the EQ-5D-5L, FACT-Leu, and the FACIT-F.

Quality of life endpoints will be summarized based on the scoring manuals for the instrument.

Sample Size Estimation:

Using the CR rate of 6% reported for current therapies* 250 subjects would provide approximately 90% power (based on an exact test for single proportions using a two-sided alpha of 5%) to reject the null hypothesis of 6% in favor of an alternative hypothesis that the CR rate for venetoclax monotherapy is 12% (doubling of the CR rate).

In order to provide approximately 80% power (based on an exact test for single proportions using a two-sided alpha of 5%) to reject the null hypothesis of 6% CR rate in favor of an alternative hypothesis that the CR rate for venetoclax monotherapy is 12% (doubling of the CR rate), the study will enroll 190 subjects who have not been previously treated with BCRi therapy. Since there are approximately a total of 250 subjects, up to 60 subjects previously treated with BCRi therapy can be enrolled.

Safety:

A safety analysis will be performed for all subjects participating in the study who took at least one dose of study drug. For the study as a whole, adverse events will be evaluated and summarized. Laboratory test results and vital signs will be explored for trends and summarized.

* Resonate Trial. ASH. 2014. Abstract 3331.

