8.1.2 Efficacy Endpoints

8.1.2.1 Primary Efficacy Endpoints

The primary efficacy endpoint will be complete remission rate (CR + CRi) of the subjects who have not been previously treated with BCRi therapy defined as the proportion of subjects achieving a CR or CRi as their best response (per the investigator assessment) based on IWCLL NCI-WG criteria.

In addition, the ninety-five percent (95%) confidence interval based on binomial distribution will be constructed for the calculated CR rate.

The assessment of response will be performed when all subjects enrolled have completed their Week 48 disease assessment, or after all enrolled subjects have discontinued venetoclax, whichever is earlier. Subjects who have not achieved complete remission (CR + CRi) prior to this time will be considered to be non-responders in the calculation of CR rate.

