8.1.2.2 Secondary Efficacy Endpoints

Key secondary efficacy endpoints will include overall response rate, duration of response, time to progression, progression-free survival, overall survival, and the CR rate in previously BCRi treated subjects.

ORR will be assessed as the proportion of subjects with an overall response (CR + CRi + nPR + PR) based on the IWCLL NCI-WG criteria. The ninety-five percent (95%) confidence interval based on binomial distribution will be constructed for the calculated CR rate.

Duration of response will be defined as the number of days from the date of first response (CR, CRi, nPR, or PR) to the earliest recurrence or PD. If a subject is still responding, then the subject's data will be censored at the date of the subject's last available disease assessment. For subjects who never experience response, the subject's data will be censored on the date of enrollment. Duration of response will be analyzed by Kaplan-Meier methodology using data for all enrolled subjects. Median duration of response will be calculated and the corresponding 95% confidence interval will be presented.

Time to progression (TTP) will be defined as the number of days from the date of first dose or enrollment if not dosed to the date of earliest disease progression. All disease progression will be included regardless whether the event occurred while the subject was taking the study drug or had previously discontinued the study drug. If the subject does not experience disease progression, then the data will be censored at the date of last available disease assessment. Data for subjects who receive non-protocol, CLL therapy prior to disease progression will be censored at the last disease assessment prior to receiving non-protocol therapy. Data for subjects without any disease assessments performed after the baseline visit will be censored at the time of enrollment plus 1 day. TTP will be analyzed by Kaplan-Meier methodology using data for all subjects enrolled. Median time TTP will be calculated and 95% confidence interval for median time TTP will be presented.

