4.3 Sample Size

Using the CR rate of 6% reported for current therapies,¹ 250 subjects would provide approximately 90% power (based on an exact test for single proportions using a two-sided alpha of 5%) to reject the null hypothesis of 6% in favor of an alternative hypothesis that the CR rate for venetoclax monotherapy is 12% (doubling of the CR rate).

In order to provide approximately 80% power (based on an exact test for single proportions using a two-sided alpha of 5%) to reject the null hypothesis of 6% CR rate in favor of an alternative hypothesis that the CR rate for venetoclax monotherapy is 12% (doubling of the CR rate), the study will enroll 190 subjects who have not been previously treated with BCRi therapy. Since there are approximately a total of 250 subjects, up to 60 subjects previously treated with BCRi therapy can be enrolled.

The power calculation was performed in nQuery Version 7.

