10.2.1 Primary Efficacy Analysis

The primary efficacy endpoint will be complete remission rate (CR + CRi) of the subjects in ITT-BN population defined in Section 5.1.1.

In addition, the ninety-five percent (95%) confidence interval based on the Clopper-Pearson exact method for binomial distribution will be constructed for the calculated CR rate.

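### Does the synopsis put the complete remission rate, and its 90% power, on the wrong population?

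*Protocol*

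**What the plan says.** The Primary Objective in the protocol synopsis sets the primary endpoint as the CR + CRi rate "of the subjects who have not been previously treated with B-cell receptor inhibitor (BCRi) therapy". Protocol 8.1.2.1 agrees: "The primary efficacy endpoint will be complete remission rate (CR + CRi) of the subjects who have not been previously treated with BCRi therapy". So does SAP 10.2.1: "The primary efficacy endpoint will be complete remission rate (CR + CRi) of the subjects in ITT-BN population", where ITT-BN is the BCRi-naive subset defined in SAP 5.1.1.2. Protocol 4.0, Protocol 5.3.3 and SAP 4.1 name the same group.

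Further down the synopsis, the efficacy definitions give the CR + CRi rate for two groups: "Defined as the proportion of subjects who achieved a CR or CRi (all subjects and previously BCRi treated subjects". The BCRi-naive group is not named there.

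The sizing text is the same in the synopsis, Protocol 8.2 and SAP 4.3. It begins with "250 subjects would provide approximately 90% power", for 6% against 12% on an exact two-sided 5% test, and attaches no population. The next paragraph repeats the hypotheses at about 80% power and says "the study will enroll 190 subjects who have not been previously treated with BCRi therapy". It then explains the total: "up to 60 subjects previously treated with BCRi therapy can be enrolled".

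The secondary list in Protocol 8.1.2.2 ends with "overall survival, and the CR rate in previously BCRi treated subjects" and does not mention an all-subject CR rate. SAP 10.2.2 plans the CR + CRi rate in the ITT and BCRi-experienced populations. SAP 10.4 plans CR + CRi subgroup analyses in the ITT population as well.

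**The concern.** The synopsis definition names two populations and neither is the primary one. The first and larger power figure appears to belong to one of those two, the all-subject group, which Protocol 8.1.2 does not list as a CR endpoint. A reader who goes no further than the synopsis could take the primary analysis to be the all-subject rate with 90% power.

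If that reading reached the report, it would matter. Up to 60 of 250 subjects, or 24% of the all-subject denominator, have had a BCRi. The documents give no separate CR rate for them, and Protocol 3.2 describes the venetoclax data after BCRi failure as limited. The all-subject rate could therefore differ from the BCRi-naive rate, and the 90% would hold only if the average over both groups were 12%.

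**Working it through.** **Inputs.** Null rate p0 = 0.06, alternative p1 = 0.12, exact single-proportion test, two-sided 5%, n = 250 and n = 190 (synopsis, Protocol 8.2, SAP 4.3). BCRi-treated subjects: up to 60, and 190 + 60 = 250.

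**Formula.** The critical count c is the smallest c with P(X ≥ c | n, 0.06) ≤ 0.025. Power is P(X ≥ c | n, 0.12).

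| n | c | upper tail at 6% | power at 12% | stated |
|---|---|---|---|---|
| 250 | 24 | 0.0163 | 0.9002 | about 90% |
| 190 | 19 | 0.0206 | 0.8311 | about 80% |

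The 250-subject figure reproduces. The 190-subject figure comes out 3.1 points above the stated value, so the plan understates it slightly. Neither statement overclaims.

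**What the 90% assumes.** Take 12% in the 190 BCRi-naive subjects and a rate r in 60 BCRi-treated subjects. The pooled rate is (190 × 0.12 + 60 × r)/250, and power is P(X1 + X2 ≥ 24) with X1 ~ Bin(190, 0.12) and X2 ~ Bin(60, r). The values of r are assumptions, because the documents give none.

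| r | pooled rate | all-subject power |
|---|---|---|
| 12% | 30.0/250 = 12.0% | 90.0% |
| 9% | 28.2/250 = 11.3% | 82.6% |
| 6% | 26.4/250 = 10.6% | 72.0% |
| 3% | 24.6/250 = 9.8% | 58.3% |

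This range runs only downward from 12%. Protocol 5.6.3 reports activity after BCRi treatment, so the documents do not settle the direction. Power for the primary group stays at 83.1% whatever r is.

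**Which text governs the primary analysis.** The synopsis definition lists rates to be analysed and calls none of them primary. The statistical methods text just before it takes all treated subjects as the analysis set except where the SAP states otherwise. The SAP does so, by defining ITT-BN and assigning the primary endpoint to it. Every place that assigns the primary endpoint names BCRi-naive subjects. The definition is therefore incomplete and does not compete with them.

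**Whether the all-subject rate is unplanned.** Protocol 8.1.2.2 introduces its list as what the key secondary endpoints include, which does not close it. Protocol 8.1 makes all enrolled subjects the default efficacy set. SAP 10.2.2 and 10.4 plan the all-subject rate explicitly.

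**The case for a change.** The strongest case for a correction is that it costs only words. The synopsis is the part most often read alone, its one CR definition leaves out the primary group, and nothing labels the 90% as belonging to another analysis. The two rates are also not interchangeable. With 12% in BCRi-naive subjects and 6% in BCRi-treated subjects, the all-subject and BCRi-naive 95% intervals fall on different sides of 6% in 13.5% of trials.

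The omission and the missing label are real. That the 250-subject sentence means all subjects is an inference from the enrolment total, but a sound one.

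The rest carries less weight. The disagreement rate counts verdicts against 6% that nobody will give, since SAP 10.1 rules out efficacy testing. Even with 12% in both groups it is 10.1%, of which 8.5 points are trials where only the larger sample clears 6%. That reflects sample size, not a difference between populations. Nor is a reader left without the primary power, because the next paragraph gives it.

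Writing a benchmark into the plan, such as 19 or more remissions among 190 for a lower limit above 6%, would not help. The count moves with the number enrolled: 18 for 169 to 181 subjects, 19 for 182 to 194, and 20 for 195 to 207. Total enrolment is only approximate, and a printed threshold would look like the decision rule that the SAP excludes.

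**Conclusion.** No change to the plan follows. The synopsis definition is incomplete and one power sentence lacks a population label. Both are clerical, and other text in the two documents resolves them.

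The stated powers are sound: 90.0% at n = 250 if the average rate is 12%, and 83.1% at n = 190 against a stated 80% or so. The weakness of the 90% figure if BCRi-treated subjects respond less often (72.0% at an assumed 6%) concerns an analysis that is not primary and will not be tested. A correction would leave the sample size, data, primary population, CR + CRi estimate and Clopper-Pearson interval as they are.

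This rests on the primary result being taken from ITT-BN as SAP 10.2.1 directs, and on the 250 in the first power sentence being total enrolment.
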